
Study Design
	
This Investigator-initiated, Treatment of High-Risk Prostate Cancer Guided by Novel Diagnostic Radio- and Molecular Tracers (THUNDER) study will be conducted in subjects with high-risk localized or locally advanced PCa. The study contains both a randomized Phase 3 treatment intensification study, and a treatment de-intensification non-randomized Phase 2 study. The aim of the THUNDER study is to improve the outcome of high-risk PCa by improved risk stratification using novel radiotracers (PSMA PET/CT) and a genomic classifier (Decipher) and subsequent treatment adaptation.
 
The hypothesis for the study is that treatment intensification based on a positive PSMA PET/ CT or Decipher high score (<math>> 0.6</math>) improves time to new metastases detected on PSMA PET/ CT in high-risk PCa.
 
In patients who are PSMA PET/ CT negative for regional or distant metastases with a low/ intermediate Decipher score (<math>\leq 0.6</math>), it is hypothesized that treatment de-intensification will improve patient quality of life while maintaining a good oncological outcome.
 
The study will be conducted at multiple centers across Europe.
 
Participation in the study will comprise a screening period, where the screening assessments must be completed before subjects are enrolled and randomized (if applicable). Eligible, consenting subjects will then undergo treatment according to their assigned study phase and treatment group, to occur over up to 96 weeks (24 months) with a post-treatment follow-up period to monitor safety and efficacy. The study will be closed 7 years from the time of randomization of the first subject.
 
The screening, treatment, and follow-up schedules are the same for both the Phase 3 and Phase 2 parts of the study, as delineated in the Schedule of Events (SOE).
 
Phase 3 Treatment Intensification Study: Patients with High-risk PCa and Positive PSMA PET/ CT and/ or Decipher high (<math>> 0.6</math>)
 
Approximately 360 evaluable patients with high-risk localized or locally advanced PCa, with PSMA positive non-localized disease or a Decipher high score (<math>> 0.6</math>) will be enrolled to the Phase 3 study. Subjects with negative PSMA PET/ CT who subsequently return a high Decipher score will also be enrolled and randomized into the Phase 3 study. All Phase 3 subjects will be randomly assigned in a 1:1 ratio to receive darolutamide plus LHRHA, or darolutamide matched placebo plus LHRHA, for up to 96 weeks (24 months). All Phase 3 subjects will also receive primary SOC RT. Subjects in Phase 3 should be commenced on an LHRHA and darolutamide or placebo within 14 days after randomization (unless started earlier) plus SOC RT for a period of approximately 1-8 weeks starting at 8–24 weeks after enrollment and randomization. Randomization of Phase 3 subjects will be stratified by 1 versus <math>> 1</math> high-risk features, N1 versus M1 PSMA positive versus PSMA negative disease, Decipher low/ intermediate versus high score, start of ADT within 4 weeks prior to randomization and clinical trial site.
 
Phase 2 Treatment De-intensification Study: Patients with High-risk PCa and Negative PSMA PET/ CT and Low/ Intermediate Decipher (<math>\leq 0.6</math>)
 
Approximately 133 evaluable patients determined to have localized PCa by PSMA PET/ CT (PSMA negative) with a low/ intermediate Decipher test score (<math>\leq 0.6</math>) will enter the non-randomized, Phase 2, single treatment arm, de-intensification study. As noted above, subjects with localized PCa by PSMA PET/ CT who return a high Decipher score (<math>> 0.6</math>) will be enrolled and randomized into the Phase 3 study. All Phase 2 study subjects will receive darolutamide for the study duration for up to 96 weeks (24 months) and primary SOC RT for a period of approximately 1-8 weeks starting at 8–24 weeks after enrollment.

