Length of Participation	On treatment: Up to 96 weeks (24 months)

	
Active Follow-Up: Follow-up visits to monitor safety and efficacy will occur as delineated in the SOE. The primary endpoint will be analysed when 96 events for the primary endpoint have been registered, which is expected to be around 7-8 years from the time of randomization of the first subject. When a subject has reached his primary endpoint, he will be transitioned to the long-term follow-up period (Post ppMFS).
 
Long term follow-up: After reaching the primary endpoint, subjects will continue to be contacted minimally every year.

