	
number, we can extrapolate the number of patients needed to be screened as only 40% of patients will have a positive PSMA scan, based on the Australian ProPSMA study (Hofman 2020) and we hypothesize that 55% of patients with a negative PSMA PET would still have a Decipher high score.
 
The following assumptions apply:
 
Based on the data from randomized trials including high-risk PCa we estimate that the 5-year FFS is 70%. In 40% of cases, a PSMA PET will detect disease outside the prostate with approximately 20% having N1 disease and 20% M1 disease. In another 30% of cases, the PSMA will be negative, but the Decipher score will still be > 0.6. We expect that the patients with a positive PET outside the prostate have a higher failure rate with current standard treatment approaches with FFS of 60% and 40% for N1 and M1 disease, respectively, or 50% combined. We expect patients with a negative PET, but Decipher high score will have a FFS of 75%. From these data, it is estimated that the combined PSMA positive or Decipher high group has a 5 year FFS of 61%. We hypothesize an increase to 76% with the addition of darolutamide.
 
Assuming proportional hazards (and for the translation from number of events to number of patients also assuming exponential FFS), the calculations were made in Power Analysis and Sample Size (PASS) software and confirmed with simulations in R.
 
 
• Accrual: 3 years
 
• Additional follow-up: 3.5 years
 
• Total duration: 3 + 3.5 = 6.5 years
 
• 5 year FFS in control arm: 61 %
 
• 5 year FFS in experimental arm 76 %
 
• Hazard ratio: 0.56
 
• Two-sided alpha of 0.05
 
• Power of 80%
 
 
With these settings, the total number of events needed is 96. For this – assuming the proportion PSMA positive and Decipher high as presented before – an estimated 306 patients need to be enrolled. With an expected dropout of 15%, this results in a requirement for 493 patients in total to be screened. In simulations, the power of the trials proved to be robust against misspecification of the PSMA positive and Decipher high proportions in the screened population – when using the number-of-events-based stopping rule.
 
Phase 2:
 
The primary endpoint for this Phase 2 study will be to detect a clinically meaningful difference in the EPIC sexual and hormonal subdomain as detected at 12 months. A comparison will be made between the patients recruited in this single arm phase 2 trial with those recruited in the phase 3 trial. This will result in comparing patients receiving either darolutamide monotherapy versus standard of care ADT and ADT plus darolutamide. We aim to measure the scores on a yearly basis to monitor late effects. We expect the baseline quality of life at inclusion will be comparable for the phase 2 and phase 3 patients as they only differ in their PSMA PET-CT result and Decipher score. Consequently, only the treatment allocation influences the quality of life.
 
Assuming an 11 points difference in the sexual domain, a standard deviation of 31.1 (based on PROSTQA) and 10% dropout/ non-compliance/ consent withdrawal incorporated group sizes of 122 (Decipher low) and 153 (SOC) and 153 (SOC+darolutamide), the estimated power is 83% (based on a t-test assuming equal variances – as the primary analysis is an analysis of covariance (ANCOVA) with group and baseline score as predictors, this can be assumed a lower bound). This 11 point difference is considered as the threshold of a minimally important difference for the sexual domain.
 
Analysis of the Primary Endpoints

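### The fixed 7-year study closure is not reconciled with a primary analysis triggered at 96 events, which the protocol expects at around 7-8 years

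*Protocol*

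**What the plan says.** All places are in the protocol synopsis.

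- **Study Design**, after the description of treatment and post-treatment follow-up: "The study will be closed 7 years from the time of randomization of the first subject". No event count is mentioned.
- **Length of Participation** makes the primary analysis depend on a count of 96 registered events, and gives this forecast for reaching it: "which is expected to be around 7-8 years from the time of randomization of the first subject". The time origin is the same as in the closure sentence.
- **Statistical Methods, sample size rationale for Phase 3**: the listed assumptions include "Accrual: 3 years", "Additional follow-up: 3.5 years" and "Total duration: 3 + 3.5 = 6.5 years". They lead to 96 events and 306 patients, and to 360 patients after allowance for 15% dropout. The same section says that power is robust to misspecified proportions of PSMA-positive and Decipher-high patients, but adds the condition "when using the number-of-events-based stopping rule".

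**The concern.** The closure sentence and the analysis trigger count from the same day but end on different conditions, one a date and the other a number of events. Apart from its first point, the forecast window for the trigger lies after the closure date. The closure sentence follows directly on the description of follow-up for safety and efficacy, so its natural meaning is that data collection ends.

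If the 96th event has not occurred by year 7, someone must choose between analysing with fewer events than planned and extending past the stated closure. That choice would come late, after the data monitoring committee has been reviewing cumulative efficacy data. The robustness statement for power would also no longer apply, because it presupposes an event-driven stop.

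A smaller mismatch is that the sample size is built on 6.5 years in total while the forecast says 7-8 years. The protocol gives no reason for the later date.

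**Working it through.** **Inputs (Phase 3 sample size rationale).** 5-year failure-free survival of 61% (control) and 76% (experimental), exponential; 1:1 allocation; accrual A = 3 years, taken as uniform (assumption); two-sided alpha 0.05; power 80%; 306 patients, no loss to follow-up.

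**1. Reproduce the 96 events.**
- Hazards per year: −ln(0.61)/5 = 0.0989 and −ln(0.76)/5 = 0.0549. Hazard ratio = ln 0.76 / ln 0.61 = 0.555.
- Freedman: d = (1.960 + 0.842)² × [(1 + 0.555)/(1 − 0.555)]² = 96.0. The stated 96 is reproduced. (Schoenfeld gives 91.)

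**2. Reproduce the 306 patients.**
- Event probability by calendar time T: p = 1 − [exp(−λ(T − A)) − exp(−λT)]/(λA).
- At T = 6.5: 0.3878 (control) and 0.2391 (experimental), mean 0.3135. 96/0.3135 = 306. The stated figure is reproduced.

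**3. Events at year 7 on these assumptions.**
- At T = 7: 0.4173 and 0.2597, mean 0.3385. 306 × 0.3385 = 103.6 events.
- Simulation (20,000 runs) gives about an 84% chance that at least 96 events have occurred by year 7.

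**4. Events at year 7 if the trigger would come later.** Since the protocol does not explain the later forecast, two explanations are used: both hazards lower by a common factor, or slower accrual with the planned hazards. Each is solved so that 306 patients yield 96 events at the stated time, and events are then counted at year 7. Power = Φ(√d × (1 − 0.555)/(1 + 0.555) − 1.960) = Φ(0.286√d − 1.960), which returns 80.0% at d = 96.

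| 96 events would arrive at | Explanation | Events at year 7 | Power |
|---|---|---|---|
| 7 years | either | 96 | 80% |
| 7.5 years | hazards × 0.83 | 89.4 | 77% |
| 7.5 years | accrual about 4.9 years | 88.0 | 77% |
| 8 years | hazards × 0.77 | 83.6 | 74% |
| 8 years | accrual about 5.8 years | 79.7 | 72% |

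Example: d = 79.7 gives 0.286 × 8.93 − 1.960 = 0.593, and Φ(0.593) = 0.72.

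**The case against.** The best defence is that year 7 is late enough on the protocol's own planning figures. The 306-patient calculation already gives about 104 events by then. The trial randomizes 360, and patients who later drop out contribute events first. If 15% loss is spread exponentially over 5 years (assumption), 96 events are expected at about 6.0 years and 112 by year 7, with about a 97% chance of at least 96. This stands: the conflict comes from the later forecast, not from the sample size section.

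The loss is also modest and biases nothing. By the Schoenfeld formula, 89 events still give 79% power and 84 give 77%. This stands too, and it limits the severity.

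Three stronger readings are tempting, and the document does not support them.
- **A reader might count three competing end rules.** The 6.5 years is a planning input for turning events into patients. It ends nothing, and it fits within a 7-year closure. Only two statements conflict.
- **A reader might infer that the later forecast concedes a lower event rate.** Multiplying the hazards by 0.83 or 0.77 would correspond to a control 5-year rate of about 66% or 68% (0.61 to the power 0.83 or 0.77), against the planned "5 year FFS in control arm: 61"%. But accrual over about 4.9 or 5.8 years produces the same delay with the planned rates unchanged, and the protocol does not say which it has in mind.
- **A reader might say the primary analysis has no valid trigger.** Length of Participation states one plainly. What is missing is a statement that it takes precedence over the closure date.

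The text available is the synopsis, so an end-of-study definition in the body of the protocol could not be checked. Even if one exists, the synopsis should agree with it.

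**Conclusion.** The inconsistency is real: an unconditional closure at 7 years stands beside an event trigger forecast at around 7-8 years from the same origin, and nothing in the text at hand says which governs. The study can close before its trigger, but it should not be inferred that it will. On the sample size assumptions closure would usually come after the 96th event, and at the lower end of the forecast the two coincide without loss.

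If the trigger would fall at 7.5 to 8 years, about 80 to 89 events would be available at year 7, and power would be about 72-77% instead of 80%, a loss of roughly 3 to 8 points. These figures assume 306 patients followed without loss, exponential survival, uniform accrual and a hazard ratio of 0.555, with either lower hazards or slower accrual as the cause of the delay. The matter should be fixed, because it concerns when the confirmatory analysis takes place and can be settled by wording. It is not a fatal flaw.

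**What to change.** Reconcile Study Design with Length of Participation in one of two ways:

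1. State that the study is not closed before the Phase 3 primary analysis at 96 events; or
2. Keep a maximum calendar time, and state which analysis is done, and with what power, if 96 events have not been reached by then.

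In either case, use one projected date for the 96th event throughout. Either carry the 6.5 years through to Length of Participation, or base the 7-8 years on stated accrual and event rates.

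**Cost.** A wording amendment. The first option may add up to about a year of follow-up beyond year 7 if the protocol's forecast holds, and more if events come more slowly, because it sets no upper limit. The second caps the duration, but accepts lower power if events are slow.

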
The following tertiary objectives will also be explored for the study:
 
 
To establish PSMA PET/ CT as a restaging tool to measure metastasis-free survival
 
To validate PSA nadir < 0.5 ng/ml as a surrogate for time to distant failure
 
To compare the failure-free survival (FFS) between the PSMA negative cohort and the PSMA positive blinded group receiving SOC treatment
 
To externally validate the results of the ProPSMA trial (Hofman 2020)
 
To report the PSMA pattern of failure in both groups
 
To compare the relapse patterns on imaging and compare them with the baseline findings (on the basis of PSMA scans taken at baseline in all patients). This will generate potential new hypothesis on treatment
 
		

intensification
 
 
To collect blood and tissue samples for biobanking.
 
To correlate findings of the Decipher genomic score with PSMA PET/ CT results.
 
 
Results for exploratory objectives of the study may be reported separately to the final clinical study report (CSR).
	

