
Intervention
	
Darolutamide and Matching Placebo
 
Study subjects allocated to receive darolutamide or matching placebo (as applicable, per study phase) will be administered the study drug as 600 mg (2 x 300mg tablets) orally twice daily for up to 96 weeks (24 months).
 
Subjects will be instructed to take tablets whole with food. If a dose is missed, the dose should be taken as soon as the subject remembers within 6 hours of the missed dose. If delayed by more than 6 hours, the missed dose should be omitted. The subject should not take 2 doses together to make up for a missed dose.
 
Subjects will receive 3 bottles of their assigned treatment at time of treatment allocation for three 28-day cycles. The first administration should occur within 14 days after treatment allocation. Following evaluation at week 12 (3 months), subjects will receive a second allocation of 3 bottles of study drug for another three 28-day cycles. These 12-week cycles are continued until determination of the primary endpoint (ppMFS) or until the maximum treatment period of up to 96 weeks (24 months).
 
Darolutamide and matching placebo will be manufactured and provided by Bayer Inc.
 
Luteinizing Hormone Releasing Hormone (Ant)-agonists
 
The choice of LHRHA is to occur at the discretion of the treating clinician. Administration of the LHRHA should be according to the product information guide. Options include, but are not restricted to, goserelin, leuprorelin, triptorelin and degarelix.
 
PSMA PET Tracer
 
All PSMA PET scans are considered as standard of care in analogy with the 2022 NCCN guidelines. All PET tracer are allowed. Patients that have undergone a PSMA PET-CT prior to entering the trial, that is not older than 3 months, are eligible to enter the trial. These patients do not need to undergo a new PSMA PET-CT.
 
Radiation Standard of Care
 
The current protocol will be as pragmatic as possible and allow multiple approved RT schedules. These schedules are applicable to all arms in the study. The RT field will be prostate only in case the risk of lymph node metastases is less than 20% as per Roach nomogram or include the whole pelvis in case the risk is > 20% even if the PSMA PET/ CT does not show pelvic nodal uptake. Patients with up to 5 M1 lesions on PSMA PET-CT, should receive SBRT to all lesions in both arms of the phase 3 trial. For delineation of the prostate, we suggest using the PACE C guidelines and for the lymph nodes the NRG guidelines (https://www.srobf.cz/downloads/nrg-oncology-updated-internati_.pdf).
 
More information in relation to RT details and regimens is provided in Appendix 4.

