--	---

	
Phase 3: ppMFS is defined as the time from randomization to the date of detection of at least 1 new PSMA-PET-positive distant lesion compared with the baseline scan or date of death from any cause. Event-free patients are censored at their last known follow-up date. ppMFS will be estimated using the Kaplan-Meier method. For the Phase 3 intensification study, the primary analysis comparing treatment arms will be a stratified log-rank test (stratified according to the randomization-strata).
 
Phase 2: EPIC mean changes in subdomain scores over time will be compared, both for change from baseline and absolute scores. The primary analysis will be an ANCOVA with group and baseline value as predictors. Given that at 1 year, the expected mortality is rather low, the primary analysis will treat deceased patients as having missing data under missing at random (MAR). As sensitivity analysis, the missing data for deceased will be imputed by worst score. An additional sensitivity analysis using trimmed means will be performed.

--	--

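### The Phase 3 sample size rests on failure-free survival, but the trial tests ppMFS, so 306 patients, 6.5 years and 80% power are not derived for the primary endpoint

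*Protocol*

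**What the plan says.** All references are to the protocol synopsis.

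**Planning inputs (Statistical Methods, sample size rationale, Phase 3).** The starting point is "Based on the data from randomized trials including high-risk PCa we estimate that the 5-year FFS is 70" per cent. PSMA-positive patients are given "FFS of 60% and 40% for N1 and M1 disease, respectively, or 50% combined". For the remaining Phase 3 patients: "We expect patients with a negative PET, but Decipher high score will have a FFS of 75" per cent. The blend of these is the control-arm figure: "From these data, it is estimated that the combined PSMA positive or Decipher high group has a 5 year FFS of 61" per cent. The experimental arm is hypothesised at 76%, which gives a hazard ratio of 0.56. The step from events to patients assumes exponential FFS. With two-sided alpha 0.05, 80% power, 3 years of accrual and 3.5 years of further follow-up, the result is 96 events and 306 patients. Allowing for 15% dropout, 493 are to be screened.

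**Endpoint tested.** In the Phase 3 paragraph under Analysis of the Primary Endpoints, the definition reads: "ppMFS is defined as the time from randomization to the date of detection of at least 1 new PSMA-PET-positive distant lesion". Whether a lesion is new is judged against the first scan, and a death from any cause also counts. On this endpoint "the primary analysis comparing treatment arms will be a stratified log-rank test".

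**FFS elsewhere.** The only other use is a tertiary objective: "To compare the failure-free survival (FFS) between the PSMA negative cohort and the PSMA positive blinded group receiving SOC treatment". FFS is not defined in the synopsis.

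**Timing.** The sample size section plans 6.5 years in total. Study Design closes the study 7 years after the first randomization. Length of Participation triggers the analysis at 96 primary-endpoint events and expects these at around 7 to 8 years.

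**The concern.** A time-to-event sample size has two parts. The number of events follows from alpha, power and the hazard ratio. The number of patients and the calendar time follow from the event rate. Here both the hazard ratio and the event rate are FFS quantities, while the log-rank test and the analysis trigger count ppMFS events. The synopsis gives no ppMFS rate, no ppMFS hazard ratio, and no argument that FFS can stand in for ppMFS.

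Two things are at stake. If the control ppMFS rate is not 61% at 5 years, 96 events will not arrive at 6.5 years. If the effect on ppMFS is not 0.56, 96 events do not give 80% power. The robustness simulations that the protocol mentions vary the proportions of PSMA-positive and Decipher-high patients. They are not described as varying the event rate or the effect.

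**Working it through.** **Step 1: reproduce the plan.** Inputs from the sample size rationale: 61% and 76% at 5 years, two-sided alpha 0.05, power 80%, 1:1 allocation, 3 years of accrual (taken as uniform), 3.5 years of further follow-up.

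- Control mix, weights 20/20/30: (20×0.60 + 20×0.40 + 30×0.75)/70 = 60.7%, stated as 61%.
- Hazard ratio: ln 0.76 / ln 0.61 = 0.555, stated as 0.56.
- Events (Freedman): (1.960 + 0.842)² × [(1 + 0.555)/(1 − 0.555)]² = 95.96, so 96.
- Event probability at 6.5 years, with yearly hazard λ = −ln S(5)/5, accrual A = 3 and follow-up F = 3.5: P = 1 − [exp(−λF) − exp(−λ(F + A))]/(λA). Control λ = 0.0989 gives 0.388; experimental λ = 0.0549 gives 0.239; the mean is 0.3135.
- Patients: 96/0.3135 = 306.3, stated as 306.
- Dropout and screening: 306/0.85 = 360. The eligible share is 0.40 + 0.60×0.55 = 0.73, and 360/0.73 = 493.

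Every stated figure reproduces from FFS inputs, so the arithmetic is sound.

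**Step 2: vary the control rate.** The document gives no 5-year ppMFS rate, so the rates below are assumptions on both sides of 61%. The hazard ratio stays at 0.555, with 306 effective patients. Power uses the same Freedman formula, inverted: Φ(√D × (1 − HR)/(1 + HR) − 1.960), with D the expected events.

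| Assumed control 5-year ppMFS | Patients for 96 events in 6.5 years | Years for 306 patients to reach 96 events | Events at 7 years | Power at 7 years |
|---|---|---|---|---|
| 55% | 264 | 5.7 | 120 | 88% |
| 61% (the FFS value) | 307 | 6.5 | 104 | 83% |
| 65% | 343 | 7.2 | 93 | 79% |
| 70% | 402 | 8.4 | 79 | 72% |
| 75% | 485 | 10.1 | 66 | 64% |

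(The 61% row shows 307 because 306.3 is rounded up.)

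**Step 3: count dropouts until they leave.** Taking 306 as the effective number ignores events in dropouts before censoring. With 360 patients and exponential dropout reaching 15% by 5 years (an assumption, since the protocol gives no time scale), year 7 yields about 100 events (82% power) at 65% and 86 events (75%) at 70%.

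**Step 4: vary the hazard ratio, keeping 96 events.** The same power formula gives 80% at 0.555, about 69% at 0.60 and about 55% at 0.65.

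**Step 5: set the timelines side by side.** The calculation gives 6.5 years, closure is at 7, and the trigger is forecast at 7 to 8. In the model of step 2, 96 events at 7 years corresponds to a control rate of about 64%, and at 8 years to about 68%. The later forecast therefore implies a lower event rate than the 61% in the calculation, unless it reflects slower accrual; the protocol does not explain the difference.

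**The case against.** The strongest reply is that the trial is event-driven. The 96 events depend on the hazard ratio and not on the base rate, so if the ppMFS hazard ratio is about 0.56 and follow-up continues to the 96th event, power holds and only the readout date moves. That stands, with two limits. The hazard ratio is itself an FFS assumption, and the stated closure at 7 years could come before the trigger. The clash between closure and trigger would exist even with correct ppMFS inputs; it matters here because it can turn a late event count into lost power.

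A reader might infer that ppMFS events must be rarer than FFS events, so that the trial is bound to fall short. The ppMFS definition does leave out local, regional and PSA-only failure. But FFS is never defined, so the document does not show what it counts beyond that, and sensitive PSMA PET imaging could bring events forward. Nor does the radiotherapy rule settle it: "Patients with up to 5 M1 lesions on PSMA PET-CT, should receive SBRT to all lesions in both arms of the phase 3 trial" concerns lesions present at baseline, whereas ppMFS counts new ones.

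A reader might also infer that all the rates were carried over from earlier trials with a different endpoint. Only the 70% is attributed to trials. The subgroup rates are expectations, 61% is their blend and 76% is a hypothesis. They could have been set with ppMFS in mind, but the protocol labels them FFS and does not say so.

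**Conclusion.** The point holds as a gap in the derivation, not as a demonstrated shortfall. The 306 patients, 6.5 years and 80% power are calculated for an undefined endpoint that the trial does not test, and the protocol gives no bridge to ppMFS. Whether this is optimistic or conservative cannot be known from the document.

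The size depends on two missing quantities. Over assumed control rates of 55% to 75%, with proportional hazards, exponential times and a hazard ratio of 0.555, the 96th event falls anywhere between 5.7 and 10.1 years. If closure at 7 years took precedence, the power loss would be small at a control rate of 65% and clear at 70%, and somewhat milder when dropouts are modelled. A weaker ppMFS effect would cost power even with all 96 events.

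This should be fixed. It falls short of a must-fix because the event trigger protects power if the hazard ratio assumption carries over and closure waits for the events.

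**What to change.** 1. Restate the Phase 3 rationale on ppMFS: assumed control and experimental 5-year ppMFS for N1, M1 and PSMA-negative/Decipher-high patients, and a ppMFS hazard ratio, each with its source or marked as an assumption. Alternatively, define FFS and justify it as a stand-in for ppMFS in both event rate and treatment effect.
2. Re-derive duration and power from these inputs, with a range on both sides of 61% and over weaker hazard ratios.
3. Keep 96 ppMFS events as the analysis trigger, unless the restated hazard ratio calls for a different number.
4. Reconcile the 6.5 years, the closure at 7 years and the forecast of 7 to 8 years, so that closure cannot precede the 96th event.
5. Add a check of the blinded pooled ppMFS event rate at the end of accrual, used to re-forecast the readout date.

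The cost is a rewritten paragraph, an amended closure rule and possibly a longer timeline. If the hazard ratio of 0.56 is retained for ppMFS and follow-up stays event-driven, no extra patients are needed. The blinded pooled check spends no alpha.
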